6.2. General Considerations

Statistical analysis of this study will be the responsibility of Eli Lilly and Company (Lilly) or its designee. All statistical analyses will be conducted with SAS Version 9.4 or higher unless otherwise stated. Any change to the data analysis methods described in the protocol will require an amendment only if it changes a principle feature of the protocol. Any other changes to the data analysis methods described in the protocol, and the justification for making the change, will be described in the SAP or the clinical study report (CSR). Some analyses and summaries described in this analysis plan may not be conducted if not warranted by data (eg, few events to justify conducting an analysis). Listings of events will be provided in such situations. Additional analyses of the data may be conducted as deemed appropriate without further changes made to the protocol or SAP, even after the final database lock (DBL).

Additionally, to avoid potential selection biases, unless stated otherwise, statistical summaries and analyses will be conducted based on randomized maintenance dose regardless of the actual treatment received by the participants. In the event of a treatment error, participants will be analyzed according to the treatment they were randomized.

There will be 2 estimands of interest in evaluating the primary and secondary efficacy objectives. The first estimand, the “efficacy” estimand, represents efficacy prior to discontinuation of study intervention and without the confounding effects of rescue therapy for severe persistent hyperglycemia. Analyses relative to the “efficacy” estimand will be conducted using the efficacy analysis set (EAS). The second estimand, the “treatment-regimen” estimand, represents the efficacy irrespective of adherence to investigational product or introduction of rescue therapy for severe persistent hyperglycemia. Analyses relative to the “treatment-regimen” estimand will be conducted using the full analysis set (FAS).

Unless specified otherwise, safety analyses for the treatment and the follow up period will be conducted relative to the “treatment-regimen” estimand using the safety analysis set (SS).

Unless specified otherwise, analysis for the lead-in period will be conducted using the lead-in analysis set (LAS).

Unless specified otherwise, the last available measurement up to Visit 6 (including unscheduled visits) collected prior to or on the first dose day will be used as the baseline for Study Period II. Unless specified otherwise, measurements prior to the first post-visit-2 insulin glargine (U100) dose will be used as the baseline for LAS.

The end of study participation for a participant will be the earliest of date of death, date of withdrawal from further participation in the study, or date of the safety follow-up visit (Visit 801). For participants considered to be lost to follow-up, end of study participation will be the date of lost to follow-up reported by the investigator. Participant data included in the database after the last date of study participation (date of death, date of early termination or date of safety follow-up) will be excluded from statistical analyses. A listing of such data may be provided.

Summary statistics for categorical measures (including categorized continuous measures) will include sample size, frequency, and percentages. Summary statistics for continuous measures will include sample size, mean, SD, median, minimum, and maximum. The summary statistics will be presented by nominal visit.

Statistical treatment comparisons will be performed between the pooled/individual tirzepatide doses and insulin lispro (U100). Comparisons among tirzepatide arms will not be performed unless specified otherwise.

Statistical summaries and results of statistical analyses will be displayed in the following treatment order: individual tirzepatide doses (5 mg, 10 mg, 15 mg) and/or pooled cohort of tirzepatide doses and insulin lispro (U100).

6.3. Adjustments for Covariates

The study is stratified by country, pre-randomization HbA1c ($\leq 8.5\%$, $> 8.5\% [\leq 69, > 69 \text{ mmol/mol}]$), and baseline metformin use (Yes/No). Where necessary to be included as a fixed effect, countries with fewer than 10 randomized participants will be pooled into one category (pooled country). For HbA1c related analyses, country/pooled country and baseline metformin use (Yes/No) will be used as fixed effects and baseline HbA1c as a covariate. For

other efficacy analyses, country/pooled country, baseline HbA1c ($\leq 8.5\%$, $>8.5\%$ [≤ 69 , >69 mmol/mol]), and baseline metformin use (Yes/No) will be used as fixed effects and respective baseline value as a covariate.

6.4. Handling of Dropouts or Missing Data

For the primary and secondary efficacy endpoint analyses relative to treatment-regimen estimand and subject to type 1 error rate control, data for participants with missing values at the 52-week visit will be imputed based on the method described in Section 6.12.1.3. For analysis relative to efficacy estimand, missing values will be considered missing at random. Unless specified otherwise, imputation of missing data will be limited to primary and key secondary efficacy endpoint analyses. Any other secondary or exploratory efficacy parameter values or safety laboratory values that are missing will not be explicitly imputed.

6.5. Multicenter Studies

To investigate potential regional influences, country/pooled country will be used as a fixed effect in statistical analyses.

6.6. Multiple Comparisons/Multiplicity

The type 1 error rate control strategy for the primary and key secondary efficacy objectives is illustrated in Section 6.12.3. No multiplicity adjustments will be made for conducting separate analyses relative to the “efficacy” and “treatment-regimen” estimands, evaluating other secondary or exploratory efficacy objectives, or safety assessments.

6.7. Patient Disposition

A summary of study disposition during the lead-in period for all enrolled patients will be provided. Reasons for screen failures will be summarized.

A listing of final study disposition and a listing of randomized treatment assignment (planned treatment) for all randomized patients will be provided. Summaries of the final study disposition and the study drug disposition for all randomized patients will be provided by planned study treatment.

6.8. Patient Characteristics

A listing of patient demographics will be provided for the enrolled population. Demographic and baseline clinical characteristics will be summarized by randomization status (yes/no) for the patients in the enrolled population using the LAS data set. A similar summary will be generated by study treatment for the patients in the modified intent-to-treat (mITT) population. Baseline demographic and clinical characteristics of special interest include: age, gender, race, ethnicity, weight, BMI, country of enrollment, HbA1c, fasting serum glucose (only for the mITT population), estimated glomerular filtration rate (eGFR), insulin glargine daily dose, pre-trial oral glucose lowering medications (SUs, DPP4is and metformin) use and duration of T2DM.

6.9. Prior and Concomitant Therapy

Prespecified concomitant medications of interest ongoing at randomization will be summarized by treatment. Medications of interest initiated after randomization and changes to medications of interest used at randomization will be summarized. Additionally, medications of interest ongoing at the beginning of the insulin glargine (U100) optimization period (Visit 2) will be summarized.

Concomitant therapies will be mapped using the World Health Organization (WHO) DRUG dictionary in the clinical trial database and will be further classified using Anatomic-Therapeutic-Chemical (ATC) codes for reporting purposes. Concomitant medication will be summarized and compared between treatment groups.

Following table provides summary of descriptive analysis that will be generated for different concomitant medications.

| Type of medication | Population | Analyses Set | ATC level | Remarks |
|---|------------|--------------|-----------|---|
| Anti-hyperglycemic medications ^a | Enrolled | LAS | 4 | Use at Visit 2 (pre-trial antihyperglycemic medications: types and doses of basal insulin, metformin, SUs and DPP4is) Summary of dose at Visit 2 will be provided at ATC 4 level |
| | mITT | FAS | 4 | Use at Visit 6 and Overall use anytime during Study Period 2 will be provided Summary of use as rescue therapy for severe persistent hyperglycemia |
| | mITT | SS | 4 | Overall use anytime during Study Period 2 or 3 will be provided |
| Anti-diarrheal medication | mITT | FAS | 4 | Initiated use during Study Period 2 will be provided |
| Anti-emetic medication | mITT | FAS | 4 | Initiated use during Study Period 2 will be provided |
| Other | mITT | FAS | 4 | -- |

Abbreviations: ATC = Anatomic-Therapeutic-Chemical; FAS = full analysis set; LAS = lead-in analysis set; mITT = modified intent-to-treat; SS = safety analysis set; SU = sulfonylureas.

^a Insulin glargine (U100) use will be included in analysis

6.10. Treatment Exposure and Compliance

A listing of patients randomized but not receiving study treatment will be provided, if applicable. The listing will include patient identification, randomized treatment arm, and the reason for not receiving study treatment (if the data is available).

A summary of duration to follow-up (defined as time in days from date of randomization to date of safety follow-up, date of early study discontinuation or date of death) and duration on study treatment (defined as time in days from first dose date to last dose date plus 7 days for tirzepatide arms; from first dose date to last dose date for insulin lispro (U100) arm) will be provided by treatment.

6.10.1. Exposure and Compliance to Tirzepatide

The number of patients and reasons for prematurely discontinuing study treatment prior to the 52-week visit will be provided by study treatment. Time-to-event analysis of premature study treatment discontinuation will be conducted.

A summary of patients who re-escalate Tirzepatide due to missing ≥ 3 doses will be provided.

Compliance to tirzepatide will be defined as taking at least 75% of the scheduled tirzepatide injections. Compliance will be calculated by taking the number of injections administered (regardless of the actual dose administered) divided by the total number of injections expected to be administered $\times 100$. Treatment compliance will be summarized descriptively for tirzepatide arms.

6.10.2. Exposure and Compliance to Insulin

6.10.2.1. Exposure to Insulin

Summary information on total daily dose of insulin glargine (U100) will be reported by visit and by treatment (tirzepatide 5 mg, 10 mg, 15 mg and insulin lispro) for the mITT population during Study Period I and II. A mixed-effect model for repeated measures (MMRM) will be used to analyze the ratio of post-baseline daily insulin glargine doses to baseline daily insulin glargine dose from randomization to Week 52 using the EAS data set. A log transformation will be performed on insulin glargine doses. The model terms will include baseline HbA1c category ($\leq 8.5\%$, $> 8.5\% [\leq 69, > 69 \text{ mmol/mol}]$), baseline metformin use (Yes/No), country/pooled country, treatment, visit, and treatment-by-visit interaction as fixed effects, and log-transformed baseline insulin glargine dose as a covariate. Summary information on total daily dose of insulin lispro (U100) will be reported by visit for the insulin lispro (U100) arm (patients who have received at least one dose of insulin lispro [U100]) during Study Period II.

If applicable, the ratio of total daily dose of insulin glargine (U100) to total daily dose of insulin lispro (U100) will be summarized by visit during Study Period II for the insulin lispro (U100) arm.

Summary information on total daily dose of insulin will be reported during Study Period II.

Unless specified otherwise, all insulin related data will be presented for both units: U and U/kg.

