If the participant achieves the target FBG per titration algorithm for 2 consecutive weeks **and** the dose of insulin glargine (U100) is low, (that is, less than 10 units), investigator may choose to temporarily interrupt insulin glargine (U100) injection. Participant should continue to measure required FBG for insulin glargine (U100) dose adjustment and be re-evaluated every 2 weeks. Insulin glargine (U100) should be restarted, if participant is not at target FBG.

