6.6. Dose Modification

6.6.1. Management of Increased Hypoglycemia Risk

If a hypoglycemic event occurs,

- participant should record in the study diary
 - BG level measured prior to administration of treatment, if taken
 - associated symptoms, and
 - treatment administered
- site personnel should educate and encourage participants to measure and record BG values during the symptoms of hypoglycemia in their study diaries, if safe to do so, and
- participants should be instructed to call the investigative site, as soon as possible, if they experience a hypoglycemic event that requires treatment assistance.

If a hypoglycemic event occurs, the investigator should

- use definitions and criteria provided in Section 8.3.7. to diagnose hypoglycemia
- properly categorize the suspected or confirmed event
- assess the effect and timing of the intervention(s)
- evaluate the frequency of the event
- establish the role of dietary changes in the development of the event
- establish the role of physical exercise, or any other contributing factor, in the development of the event, and

- provide participant additional education, if deemed appropriate.

Investigators are responsible for their participant's management and well-being. Therefore, it is their responsibility to implement these generally recommended measures, or to modify them, taking into account clinical and other relevant criteria.

Management of hypoglycemia in participants in tirzepatide arms

- In the absence of obvious causes (such as dietary or physical activity changes) of hypoglycemia, dose of insulin glargine (U100) should be adjusted first to manage increased risk of hypoglycemia. In case of repeated hypoglycemic events, even with a low insulin glargine (U100) dose (that is, less than 10 units/day) and despite insulin glargine (U100) dose decreases per the titration algorithm, administration of insulin glargine (U100) may be temporarily or permanently discontinued.
- Participant should be restarted on insulin glargine (U100), whenever it is safe to do so per clinical judgement of investigator.
- Metformin dose, if applicable, may also be reduced or discontinued if increased hypoglycemia risk persists, but only after appropriate adjustment of insulin glargine (U100).

Management of hypoglycemia in participants in the insulin lispro (U100) three times a day arm

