- In the absence of obvious causes (such as dietary or physical activity changes) of hypoglycemia, timing of the hypoglycemic event(s) should be consulted and dose of insulin glargine (U100) and/or insulin lispro (U100) should be adjusted first to manage increased risk of hypoglycemia.
- If the participant experiences repeated hypoglycemia in spite of decreasing insulin glargine (U100) dose to a low level (less than 10 units), investigator may choose to temporarily or permanently discontinue insulin glargine (U100).
- If the participant experiences repeated hypoglycemia in spite of decreasing the relevant insulin lispro (U100) dose of the day to a low level (less than 4 units), investigator may choose to temporarily interrupt that particular dose of insulin lispro (U100). Remaining doses of insulin lispro (U100) for the day may be continued based on the clinical judgement of the investigator.
- Participant should be restarted on insulin glargine (U100) and/or regular TID regimen of insulin lispro (U100), whenever it is safe to do so per clinical judgement of investigator.
- Metformin dose, if applicable, may also be reduced or discontinued if increased hypoglycemia risk persists, but only after appropriate adjustment of insulin glargine (U100) and/or insulin lispro (U100).

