7.1.1. Temporary Discontinuation

In certain situations, after randomization, the investigator may need to temporarily interrupt study intervention(s). Every effort should be made by the investigator to maintain participants on study intervention(s) and to restart after any temporary interruption, as soon as it is safe to do so.

The data related to temporary interruption of study intervention(s) will be documented in source documents and entered on the eCRF.

Temporary discontinuation of tirzepatide

This shows how to manage treatment if there are missed tirzepatide doses.

Table 12. Managing Missed Tirzepatide Doses

If the number of missed tirzepatide doses is...	Then...
2 or less	treatment can be restarted at the same dose, if tirzepatide was well tolerated prior to interruption.
3 or more	the IWRS will dispense 5 mg tirzepatide irrespective of the dose the participant was receiving before the interruption and subsequently escalate as required by protocol.

Abbreviations: IWRS = interactive web-response system.

If tirzepatide interruption is due to intolerable persistent GI AE, such as nausea, vomiting, or diarrhea, the participant should be treated as suggested in Section [6.6.3](#).

Temporary discontinuation of insulin lispro (U100) three times a day

See Section [6.6.1](#). for management of increased hypoglycemia risk and temporary discontinuation of insulin lispro (U100).

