At Visit 6, participants will undergo all required baseline study procedures (including the collection of all baseline laboratory measures, vital signs, electrocardiogram (ECG), and questionnaires) prior to randomization and prior to injecting their first dose of study intervention, tirzepatide or insulin lispro (U100).

All participants, randomized to either tirzepatide or insulin lispro (U100) TID, will **reduce their dose of insulin glargine (U100) by 30% at Visit 6** to reduce the potential risk of hypoglycemia and safely introduce tirzepatide or insulin lispro (U100) and follow titration instructions for insulin glargine (U100) treatment. Participants will follow dose-escalation schemes for tirzepatide or titration instructions for insulin lispro (U100) thereafter.

End of Visit 6 to Visit 23 (Post-Randomization)

Insulin Glargine (U100)

For participants in the tirzepatide arms, dose of insulin glargine (U100) will remain unchanged after the initial 30% dose reduction at Visit 6 until 4 weeks after randomization (ie, until Visit 10) except for safety reasons (ie, hypoglycemia/severe hyperglycemia). Participants will initiate insulin glargine (U100) titration after Visit 10 per protocol-defined Insulin Glargine (U100) Titration Algorithm.

For participants in the insulin lispro (U100) arm, participants will initiate titration of insulin glargine (U100) after Visit 6 per protocol-defined Insulin Glargine (U100) Titration Algorithm.

For insulin glargine (U100) titration, all participants should adjust insulin glargine (U100) dose weekly. Participants will be instructed to adjust insulin glargine (U100) doses to a targeted FBG of 100 to 125 mg/dL (5.6 to 6.9 mmol/L). If the participant achieves the target FBG per titration algorithm for 2 consecutive weeks and the dose of insulin glargine (U100) is less than 10 units, investigator may choose to temporarily interrupt insulin glargine (U100) injection.

Tirzepatide

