6.1. Populations for Analyses

For purposes of analysis, [Table GPHD.6.1](#) defines the following analysis populations/data sets.

Table GPHD.6.1. Analysis Populations/Data Sets

| Population/Data Set | Description |
|---|--|
| Screened population | All participants who sign informed consent |
| Enrolled population | All participants who are exposed to at least 1 dose of insulin glargine (U100) after Visit 2 |
| Randomized population | All participants who are randomly assigned a treatment arm |
| Safety Population | All randomly assigned participants who are exposed to at least 1 dose of study drug (tirzepatide or insulin lispro [U100]). |
| Modified intention-to-treat (mITT) population | All randomly assigned participants who are exposed to at least 1 dose of study drug (tirzepatide or insulin lispro [U100]), excluding inadvertently enrolled participants who have discontinued study drug for that reason. |
| Lead-in analysis set (LAS) | Data obtained during Study Period I, after first dose of insulin glargine (U100) after Visit 2 and prior to the first dose of tirzepatide or insulin lispro (U100) (or Visit 6 date if the dose date is missing). |
| Efficacy analysis set (EAS) | Data obtained during Study Period II from the mITT population, excluding data after initiating rescue antihyperglycemic medication or early discontinuation of study drug (tirzepatide: last dose date + 7 days; insulin lispro (U100): last dose date). |
| Full analysis set (FAS) | All available data obtained during Study Period II, regardless of adherence to study drug or initiation of rescue antihyperglycemic medication. |
| Safety analysis set (SS) | All available data obtained during Study Periods II and III regardless of adherence to study drug or initiation of new antihyperglycemic medication. |

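### The log-dose model for insulin glargine (SAP 6.10.2.1) has no rule for 0 U, a dose the protocol permits while study drug continues

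*SAP*

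**What the plan says.** SAP 6.10.2.1 models the post-baseline to baseline ratio of daily glargine dose from randomization to Week 52 by MMRM on the efficacy analysis set. It states that "A log transformation will be performed on insulin glargine doses" and uses the log baseline dose as covariate. It names no offset, floor or other treatment of a zero dose. The same section promises a by-visit, by-arm summary of total daily glargine dose in U and U/kg.

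Glargine can be at 0 U in every arm while study drug continues:

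- Protocol 6.1.2.2.1: once fasting glucose has been at target for two weeks on less than 10 units, the "investigator may choose to temporarily interrupt insulin glargine (U100) injection". SAP 5.1 repeats this: "the dose of insulin glargine (U100) is less than 10 units, investigator may choose to temporarily interrupt insulin glargine (U100) injection".
- Protocol 6.6.1, tirzepatide arms: for repeated hypoglycemia at a low dose, "administration of insulin glargine (U100) may be temporarily or permanently discontinued". The lispro arm has the same option.

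The efficacy analysis set (SAP 6.1) removes data only by "excluding data after initiating rescue antihyperglycemic medication or early discontinuation of study drug", with last-dose rules for tirzepatide and lispro alone. SAP 6.4 adds: "For analysis relative to efficacy estimand, missing values will be considered missing at random". It limits explicit imputation to primary and key secondary endpoints.

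**The concern.** The stated transformation is undefined at a dose that the protocol allows on treatment. A visit at 0 U is an observed outcome, and it is the largest reduction a participant can have. If the model drops it and fills the gap under missing at random, it predicts a positive dose where none was taken. Values lost because they are the lowest possible are not missing at random.

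At stake is the only modelled comparison of background insulin between arms. Its estimate would describe a setting in which everyone still injects glargine, and nothing in the planned output would tell the reader so.

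**Working it through.** The plan states no figure for this analysis and no expected share at 0 U, so there is nothing to reproduce.

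**1. Can 0 U be reached?** Inputs: basal dose of at least 30 U/day at entry (Protocol 5.1, criterion 2), a 30% cut at Visit 6 (6.1.2.2.1) and a weekly 2-unit decrease for median fasting glucose of 71 to 99 mg/dL (Table 7). For a participant at the entry minimum with no dose change before Visit 6: 30 × 0.70 = 21 U, and 21 − 6 × 2 = 9 U, below the 10-unit level. So it is possible; this does not say how often.

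**2. Do these visits stay in the analysis set?** Yes. Stopping glargine is neither rescue nor discontinuation of study drug. Baseline doses are positive, so only post-baseline records are affected.

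**3. What does the model do with them?** The log of 0 divided by baseline is undefined. The dataset might hold 0 or a blank (both missing in a plain log model) or the last prescribed dose (a positive value). In none of these cases is the zero counted.

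**4. Direction.** Let p be the share at 0 U and g the dose ratio among the rest. A log analysis of the remaining records reports a reduction of 1 − g whatever p is. If every non-zero participant is at g, the mean ratio with zeros is (1 − p)g. At g = 0.5 the log analysis reports 50%. With zeros the reduction is 1 − 0.95 × 0.5 = 52.5% at p = 5%, and 1 − 0.90 × 0.5 = 55.0% at p = 10%. An MMRM recovers part of the gap from earlier visits but can only predict positive doses.

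**5. Size under an MMRM.** All inputs here are assumptions. The simulation used 150,000 per group, five post-baseline visits, unstructured covariance and log baseline dose as covariate. Baseline geometric mean was 45 U before truncation at 30 U or more (log SD 0.39). Lispro had latent ratio 1.0 (log SD 0.4) and almost no zeros. A tirzepatide visit is 0 U if its latent dose is below 10 U and the participant is one who stops. Log SD on tirzepatide was 0.6 (A) or 0.7 (B). Results at visit correlation 0.9, for a gradual fall in mean dose and for a constant mean:

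| Scenario | At 0 U, Week 52 | Fitted ratio | Against latent |
|---|---|---|---|
| A, latent 0.60 | 2.5% | 0.608, 0.612 | +1.3%, +2.0% |
| A, latent 0.60 | 5.0% | 0.616, 0.624 | +2.7%, +4.0% |
| B, latent 0.40 | 4.6% | 0.410, 0.413 | +2.5%, +3.3% |
| B, latent 0.40 | 9.1% | 0.419, 0.431 | +4.8%, +7.8% |

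Separately coded constant-mean fits gave 0.627 (A, 5%; 0.627/0.60 = 1.045) and 0.434 (B, 9%; 0.434/0.40 = 1.085). Varying the visit correlation from 0.6 to 0.95 gives 0.614 to 0.627 (A) and 0.416 to 0.434 (B), so the lowest excess is 0.614/0.60 − 1 = 2.3%.

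**6. Dependence on where the zeros fall.** With equal zeros and equal latent doses the between-arm ratio is 1.00, but each arm's own ratio to baseline is 0.616 to 0.625 against 0.60 (5%) or 0.419 to 0.432 against 0.40 (9%). With 5% zeros on lispro only and equal latent doses the ratio is 0.964 instead of 1.00, which flatters tirzepatide.

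**7. Against precision.** The log-scale 95% half-width, 1.96 × √((SD₁² + SD₂²)/591), is 0.055 (A) and 0.062 (B) for the pooled comparison. For one dose (197 vs 591, lispro SD 0.4) it is about 0.084 and 0.097. The largest log biases are ln(0.627/0.60) = 0.044 and ln(0.434/0.40) = 0.082. Only the second exceeds a half-width, and only for the pooled comparison. On the original scale, dropping zeros moves the difference from −19.6 U to between −18.6 and −19.2 U (A, 5%) and from about −30.8 U to between −29.2 and −30.1 U (B, 9%). The half-width there is about 3 U.

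**The case against.** **The SAP does not say that zeros become missing.** Correct. That follows from a plain log and a software default, and from a dataset that holds 0 or a blank. If it holds the last prescribed dose, nothing goes missing; the problem is then one of recording, which an untransformed model would share. What the text supports is that no rule exists.

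**The zeros may not be recorded.** A reader might take Protocol 7.1.1 ("The data related to temporary interruption of study intervention(s) will be documented in source documents and entered on the eCRF") as proof that glargine interruptions are captured. It is weak support: its operative paragraphs cover tirzepatide and lispro, Table 15 equates study intervention with those two, and Table 6 calls glargine a background intervention. Protocol 4.1.1.2 is better support, because the diary collects glargine doses and dose adjustments throughout treatment.

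**The bias is measured against an invented benchmark.** This stands. A geometric mean ratio does not exist when some doses are 0, and the latent ratio is a simulation device. Other conventions give other sizes. In a different simulation with 30% zeros assumed, the MMRM gave a 70.5% reduction, against 84.3% with zeros set to 1 U and 87.3% with 0.5 U. That spread is itself a reason to fix the handling in advance.

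**The dose summary already covers it, and SAP 6.2 allows further analyses.** Partly. If zeros are recorded as 0, the by-visit mean, median and minimum retain them. There is no count at 0 U, though, and the table does not correct the model. Analyses added later are not prespecified.

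**Conclusion.** The gap is real and minor. A specified transformation cannot be applied to a permitted on-treatment dose, and the default consequence understates the glargine reduction in any arm that has zeros. For the illustrative rates of 5% to 9% at 0 U in one arm, the tirzepatide to lispro ratio is about 3% to 9% too high at visit correlation 0.9 (2.3% at the lowest over the correlations tried). No scenario reverses the direction. These sizes rest on assumed zero rates, dose distributions and a latent-dose benchmark; the documents supply none of them.

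Three stronger readings are tempting and not supported. One is that every arm's reduction is understated: an arm without zeros is unaffected. Another is that the tirzepatide effect on insulin dose is necessarily understated: if zeros are commoner on lispro, it is overstated. The third is that efficacy conclusions are at risk: this exposure model lies outside the objectives and type 1 error control, and the HbA1c and body-weight analyses do not use it.

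**What to change.** Amend SAP 6.10.2.1 as follows:

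1. State that interrupted or stopped glargine is analysed as 0 U at that visit, using the diary doses.
2. Report the number and proportion at 0 U by visit and arm alongside the existing dose summary.
3. Add an analysis of change from baseline in daily glargine dose on the original scale (U and U/kg), zeros kept, with the same fixed effects and the untransformed baseline dose as covariate.
4. If the log-ratio MMRM is kept, state how 0 U records are handled and that its estimate assumes a positive dose for everyone. It is not an estimate among those still injecting: in the simulation that ratio was 0.637 (A, 5%) and 0.439 (B, 9%).

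The cost is a few lines of text, one model and one extra row per visit in an existing table. The drawback is more skewed residuals on the original scale. In 4,000 simulated trials per setting, a Week 52 ANCOVA with zeros kept had 95% interval coverage of 94.5% to 95.6%, for 591 vs 591 and 197 vs 591. A repeated-measures version was not tested, so its coverage should be checked if that form is chosen. All four items concern analysis only and change nothing in how glargine is managed.
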